2. INTRODUCTION

This is a Phase 1, first-in-human (FIH), randomized, double-blind, placebo-controlled study to evaluate the safety and PK of single ascending doses (SAD) of VT-1598 administered in healthy adult subjects among 6 cohorts (5 fasted cohorts, 1 fed cohort). Each cohort contains 8 subjects (N = 8), 6 subjects will be given an oral dose of VT-1598 and 2 subjects will receive placebo.

2.1. Purpose of the Analyses

This SAP describes safety and PK analyses of 40 mg, 80 mg, 160 mg, 320 mg, and 640 mg of VT-1598 given orally under a fasted state; and of 160 mg of VT-1598 given orally under a fed state (after administration of a high-fat, high calorie meal). PK analyses include assessment of VT-1598 and its primary metabolite, VT-11134.

3. STUDY OBJECTIVES AND ENDPOINTS

3.1. Study Objectives

Primary:

- To determine the safety of single-ascending oral doses of VT-1598 in healthy adult subjects in a fasted state.
- To determine the safety of a single oral dose of VT-1598 in healthy adult subjects in a fed state.

Secondary:

- To determine the PK profile in plasma and urine of VT-1598 and its primary metabolite, VT-11134, in healthy adult subjects.
- To determine the effect of a high-fat, high-calorie meal on the PK profile of VT-1598 and VT-11134 when a single oral dose of VT-1598 is given.

3.2. Endpoints

Primary:

- Safety will be evaluated for single-ascending fasting oral doses of VT-1598. Safety will be assessed by adverse events (AE) from start of dosing to Day 21, clinical laboratory tests at baseline and from Day 4 to Day 21, vital signs (VS) at baseline and from Day 1 to Day 21, and electrocardiogram (ECGs) at baseline and on Day 1, Day 4, and Day 21;
- Safety will be evaluated for single oral dose of VT-1598 administered after being fed a high-fat, high-calorie meal. Safety will be assessed by adverse effects from start of dosing to Day 21, clinical laboratory tests at baseline and from Day 4 to Day 21, VS at baseline and from Day 1 to Day 21, and ECGs at baseline and on Day 1, Day 4, and Day 21.

Secondary:

- PK profiles of VT-1598 and its primary metabolite, VT-11134, will be assessed by measurement of VT-1598 and VT-11134 levels in both plasma and urine after VT-1598 administration in each cohort, when fasting. Plasma for PK analysis will be collected at planned timepoints up to 480 hours post dose and urine for PK analysis will be collected in planned intervals up to 72 hours post dose.
- PK profiles of VT-1598 and its primary metabolite, VT-11134 will be assessed by measurement of VT-1598 and VT-11134 levels in both plasma and urine after administration of VT-1598 following consumption of a high-fat, high-calorie meal. Plasma for PK analysis will be collected at planned timepoints up to 480 hours post dose and urine for PK analysis will be collected in planned intervals up to 72 hours post dose.

3.3. Study Definitions and Derived Variables

3.3.1. Cohort

Cohort in the SAP will be defined to match identically with cohort as defined in the protocol ([Table 1](#)).

Fasted cohorts:

- Cohort 1: Single 40 mg tablet of VT-1598 (6 subjects) or matching placebo (2 subjects)
- Cohort 2: Two 40 mg tablets (80 mg total) of VT-1598 (6 subjects) or matching placebo (2 subjects)
- Cohort 3: Four 40 mg tablets (160 mg total) of VT-1598 (6 subjects) or matching placebo (2 subjects)
- Cohort 4: Four 80 mg tablets (320 mg total) of VT-1598 (6 subjects) or matching placebo (2 subjects)
- Cohort 5: Eight 80 mg tablets (640 mg total) of VT-1598 (6 subjects) or matching placebo (2 subjects)

Fed cohort:

- Cohort 6: Four 40 mg tablets (160 mg total) of VT-1598 or matching placebo, following a high-fat, high-calorie meal. Cohort 6 will be comprised of the same subjects as Cohort 3 who will be assigned the same treatment arm as randomized in Cohort 3. Subjects who complete Cohort 3 but withdraw or become ineligible prior to dosing for Cohort 6 will be replaced. The Cohort 6 replacement subjects will receive the same study product as assigned to the Cohort 3 subject they are replacing.

3.3.2. Dose Group

Dose Group defines a grouping of subjects for statistical analysis, where subjects within a Dose Group receive the same study product and dose under the same fasting status. Two combined Dose Groups, the Any Dose and Placebo Dose Groups, will include all subjects who receive the same study product (VT-1598 or Placebo, respectively) regardless of the subject's fasting status. Subjects who participate in both Cohort 3 and Cohort 6 will be counted separately for each dosing period based on the study product received. Any summary tables including a column for 'All Subjects' will also count Cohort 3 and Cohort 6 subjects separately for each dosing period. For data from a subject to be analyzed as part of their Dose Group, the subject must also qualify for inclusion into the respective analysis population (Section 6.3). The Dose Groups in the order they will be presented are defined as follows:

- Any Dose: All subjects who received a complete or incomplete dose of VT-1598 regardless of fasting status. Subjects who received VT-1598 in Cohort 3 and continued to Cohort 6 will be included in the Any Dose Group separately for each dosing period.
- 40 mg Fasted: Cohort 1 subjects who received a complete dose of active drug under a fasted state.
- 80 mg Fasted: Cohort 2 subjects who received a complete dose of active drug under a fasted state.
- 160 mg Fasted: Cohort 3 subjects who received a complete dose of active drug under a fasted state.
- 160 mg Fed: Cohort 6 subjects who received a complete dose of active drug following a high-fat, high-calorie meal.
- 320 mg Fasted: Cohort 4 subjects who received a complete dose of active drug under a fasted state.
- 640 mg Fasted: Cohort 5 subjects who received a complete dose of active drug under a fasted state.
- Placebo: All subjects who received a complete or incomplete dose of placebo, regardless of fasting status. Subjects who received placebo in Cohort 3 and continued to Cohort 6 will be included in the Placebo group separately for each dosing period (unless replaced as detailed in Section 4.4.3).

Analyses by Dose Groups will be presented in the following order: Any Dose (when included), 40 mg Fasted, 80 mg Fasted, 160 mg Fasted, 160 mg Fed, 320 mg Fasted, 640 mg Fasted, and Placebo.

In the unlikely case that a subject is given the wrong dose, that subject may be analyzed based on actual dose received or with a different Dose Group than those described above. Reasoning for assigning the subject to a different Dose Group will be described in the CSR. The “Any Dose” group will be included in the analyses of safety endpoints only.

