4.2. Discussion of Study Design, Including the Choice of Control Groups

DMID Protocol 17-0087 is designed as a placebo-controlled double-blinded dose escalation trial with 2 subjects randomized to placebo and 6 subjects randomized to active drug per cohort. The dose escalation design is utilized to confirm the safety of low doses prior to exposing subjects to high doses. Subjects who successfully complete Cohort 3 will “rollover” to Cohort 6 after a minimum of 60 days following their first dose after completion of Cohort 3. As part of Cohort 6, subjects will be given the study product following a high-fat, high-calorie meal to study the safety and PK profiles of VT-1598 and VT-11134, its primary metabolite, under a fed state. This is intended to provide a preliminary assessment of whether there is a food effect. Comparisons of fed to fasted PK profiles will be exploratory. For comparisons of active drug Dose Groups to placebo, a pooled group of placebo subjects across multiple cohorts will be used. The same subjects assigned to placebo in Cohort 3 that continue to Cohort 6 will be counted separately within the Placebo Dose Group for each dosing period.

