6.3.1. Safety Population

The Safety Population will include all subjects that received any amount of study product and will be analyzed by Dose Group. Placebo subjects will be pooled across multiple cohorts for analysis. Placebo

subjects enrolled in Cohort 3 that continued on to Cohort 6 will be counted separately for each study part, as detailed in Section 3.3.2.

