9. SAFETY EVALUATION

All safety analyses will be performed using the Safety Population and will be presented by Dose Group. Placebo subjects enrolled in Cohort 3 that continued on to Cohort 6 will be counted separately for each dosing period, as detailed in Section [3.3.2](#).

Any medical condition that is present at the time that the subject is screened will be considered baseline and not reported as an AE, unless it worsens in severity or increases in frequency during the study. The denominators for proportion values will be indicated within the table or table header. AEs will be summarized for the number of subjects who experienced an AE and the number of events by Dose Group and Medical Dictionary for Regulatory Activities (MedDRA®) category. Toxicity grading scales for clinical adverse events are provided in All reported AEs will be included in the summaries and analyses.

Clinical laboratory, VS, and ECG results will also be used to assess safety. Results from these assessments will be graded by severity and presented in tables and figures by Dose Group for each post baseline timepoint. The analysis timepoints that will be summarized are presented in [Table 7](#). The most extreme severity grade observed after dosing will be summarized (Maximum Severity Post Baseline) and will include results from unscheduled visits. For tabular displays of clinical laboratory, VS, and ECG results by parameter, the maximum severity across all parameters within each category (CHEM, HEM, COAG, UA, VS, and ECG) will be included and summarized by timepoint (Any Parameter). CHEM, WBC (in COAG), and VS parameters will be displayed by event direction (increase or decrease).

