9.3.2. Unsolicited Adverse Events

An overall summary of unsolicited AEs by Dose Group will be presented in [Table 17](#) including the number of subjects with at least one AE, number of subjects with at least one related AE, and number of subjects with at least one SAE.

All AEs will be presented in [Listing 11](#). A subject listing of non-serious AEs of moderate or greater severity will also be reported ([Table 22](#)).

Denominators for proportions are the number of subjects in the Safety Population in each Dose Group. Placebo subjects who participated in both Cohort 3 and Cohort 6 will contribute to the denominator once per each dosing period for the Placebo Dose Group. Subjects who received VT-1598 and participated in both Cohort 3 and Cohort 6 will contribute to the denominator once per each dosing period for the Any Dose Group. The following summaries for unsolicited AEs will be presented:

- The number of AEs and number and proportion of subjects reporting an AE or SAE that occurred in 5% of all subjects along with the total number of events reported will be presented by Dose Group, SOC, HLTG, and preferred term (PT) ([Table 18](#)).
- The number of AEs and number and proportion of subjects reporting an AE will be presented by Dose Group, SOC, HLTG, and PT. The 95% CI for the proportion of subjects experiencing each SOC/HLTG/PT will also be presented ([Table 19](#)).
- The number and proportion of subjects reporting a related or unrelated AE will be presented by Dose Group, SOC, HLTG, PT, severity, and relationship to study product. ([Table 20](#))

Summaries of unsolicited AEs will be presented graphically in bar charts by Dose Group and SOC. For summaries of proportions of subjects reporting an AE, denominators will be the number of subjects in the Safety Population for each Dose Group. Placebo subjects who participated in both Cohort 3 and Cohort 6 will

contribute to the denominator once per each dosing period. Subjects who received VT-1598 and participated in both Cohort 3 and Cohort 6 will contribute to the denominator once per each dosing period for the Any Dose Group:

- The proportion of subjects reporting a related AE will be presented by the maximum severity reported per SOC ([Figure 3](#)).
- The total number of related AEs reported will be presented by Dose Group and SOC ([Figure 4](#)).

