Analysis Populations	Reason Subjects Excluded	40 mg Fasted (N=X)	80 mg Fasted (N=X)	160 mg Fasted (N=X)	160 mg Fed (N=X)	320 mg Fasted (N=X)	640 mg Fasted (N=X)	Placebo (N=X)	All Subjects (N=X)
		n (%)	n (%)	n (%)	n (%)	n (%)	n (%)	n (%)	n (%)
Safety Population	No study product received	x (x)	x (x)	x (x)	x (x)	x (x)	x (x)	x (x)	x (x)
PK Analysis Population	Any reason	x (x)	x (x)	x (x)	x (x)	x (x)	x (x)	x (x)	x (x)
	Subject received placebo	x (x)	x (x)	x (x)	x (x)	x (x)	x (x)	x (x)	x (x)
	Assigned dose not received or completed	x (x)	x (x)	x (x)	x (x)	x (x)	x (x)	x (x)	x (x)
	Subject has no measurable concentration in plasma or urine at any timepoint	x (x)	x (x)	x (x)	x (x)	x (x)	x (x)	x (x)	x (x)
PK Analysis Subset	Any reason	x (x)	x (x)	x (x)	x (x)	x (x)	x (x)	x (x)	x (x)
	Excluded from PK Analysis Population	x (x)	x (x)	x (x)	x (x)	x (x)	x (x)	x (x)	x (x)
	Protocol deviation(s) with potential to impact PK	x (x)	x (x)	x (x)	x (x)	x (x)	x (x)	x (x)	x (x)
	PK data insufficient to estimate any PK parameters	x (x)	x (x)	x (x)	x (x)	x (x)	x (x)	x (x)	x (x)

Notes: N=Number of subjects enrolled/randomized.

Results from subjects in Cohort 3 that continued on to Cohort 6 are summarized separately for each dosing period in the All Subjects and Placebo columns.

Table 11: Ineligibility Summary of Screen Failures

[Implementation Note: Although subjects may meet multiple criteria for exclusion, each subject will only be counted under one reason for exclusion in this table. The final summary table will include only inclusion/exclusion criterion with at least 1 subject. Criteria that were not met by any subjects will be excluded from final table. If any of the criteria footnotes change in subsequent versions of the study protocol, the updated text should be used instead.]

Inclusion/Exclusion Category	Inclusion/Exclusion Criterion	Subjects Excluded	
		n ^a	% ^b
Inclusion and Exclusion	Number of subjects failing any eligibility criterion	x	100
Inclusion	Any inclusion criterion	x	xx
	Willing and able to provide written informed consent and authorization for use of protected health information	x	xx
	Willing and able to comply with protocol requirements, instructions, and protocol-stated restrictions (including confinement to the CRU) and is likely to complete the study as planned	x	xx
	Male and female subjects, 18-45 years of age (inclusive)	x	xx
	Subject is in good health to be safely enrolled in this protocol and determined by medical history and physical exam		

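### An active subject who takes only part of the dose drops out of every dose-level safety column, while a partial placebo doser stays in the Placebo column

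*SAP*

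**What the plan says.** SAP 3.3.2 lists eight Dose Groups. The six active dose-level groups (40, 80, 160 fasted, 160 fed, 320 and 640 mg) share one condition, as in "640 mg Fasted: Cohort 5 subjects who received a complete dose of active drug under a fasted state". The two pooled groups are wider. Placebo is defined as "Placebo: All subjects who received a complete or incomplete dose of placebo, regardless of fasting status", and Any Dose uses the same complete-or-incomplete wording for VT-1598.

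The safety analyses are built on these groups:

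- SAP 6.3.1: "The Safety Population will include all subjects that received any amount of study product and will be analyzed by Dose Group".
- SAP 9: "All safety analyses will be performed using the Safety Population and will be presented by Dose Group".
- SAP 9.3.2, for adverse events: "Denominators for proportions are the number of subjects in the Safety Population in each Dose Group".
- SAP 4.2, on the control: "For comparisons of active drug Dose Groups to placebo, a pooled group of placebo subjects across multiple cohorts will be used".

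SAP 3.3.2 closes with a provision for a subject given the wrong dose: "that subject may be analyzed based on actual dose received or with a different Dose Group than those described above". The reasoning is to be given in the CSR.

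Protocol 10.5 defines the safety population by receipt of any quantity of product, analysed according to the treatment taken. It does not require the dose to be completed.

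**The concern.** The completeness condition applies to the active dose columns and not to the placebo column they are read against. A subject who starts an active dose and does not finish it stays in the Safety Population and in Any Dose, but meets no dose-level definition. A subject who does the same on placebo is still counted.

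Stopping part-way can itself be a tolerability event. If it is, it goes missing from the column of the dose being judged, in a study whose primary endpoint is the safety of ascending single doses. With six active subjects per column, losing one is visible in both numerator and denominator.

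**Working it through.** **1. Where each kind of subject goes under SAP 3.3.2 as written**

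| Subject | Safety Population | Dose-level column | Pooled column |
|---|---|---|---|
| Active, complete dose | yes | yes | Any Dose |
| Active, partial dose | yes | none | Any Dose |
| Placebo, complete dose | yes | not applicable | Placebo |
| Placebo, partial dose | yes | not applicable | Placebo |

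Any Dose against Placebo is like for like. Each dose level against pooled placebo is not.

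**2. Consistency within the SAP**

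- The Table 10 shell prints a row for "Assigned dose not received or completed" and a row for no product received under every dose-level column, with N defined as subjects enrolled or randomized. Under 3.3.2 undosed and partly dosed subjects are not in those columns, so both rows can only be zero there.
- The Dose Group orders for the serious AE, moderate or severe AE and abnormal laboratory listings contain the six dose levels and Placebo, with no Any Dose slot. A partial active doser would be listed with no defined group label.
- SAP 6.3.2 already removes incomplete doses from the Dose Groups for PK, so the restriction in 3.3.2 is not needed for that purpose.

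**3. Does the wrong-dose provision close the gap?** No. It is written for a subject given the wrong dose, it is permissive, and it leaves the choice to the reporting stage. SAP 6.3.2 can be read as treating an incomplete dose as one kind of incorrect dose. Even so, the provision would only allow reassignment, not require it.

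**4. Size, for one assumed partial doser**

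The plan has no figure of its own to reproduce on this point. The inputs are 6 active subjects per cohort in 6 cohorts (SAP 2) and exact Clopper-Pearson 95% intervals (SAP 6.1). I assume that one active subject takes part of the dose and has an adverse event, and that no one else in that column has one.

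The lower limit is the 0.025 quantile of Beta(x, n − x + 1). The upper limit is the 0.975 quantile of Beta(x + 1, n − x). For x = 0 the lower limit is 0 and the upper limit is 1 − 0.025^(1/n).

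| Column | x/n | Proportion | 95% CI |
|---|---|---|---|
| That dose, any quantity counted | 1/6 | 16.7% | 0.4% to 64.1% |
| That dose, as written | 0/5 | 0% | 0% to 52.2% |
| Any Dose | 1/36 | 2.8% | 0.07% to 14.5% |

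Column totals: 6 × 6 = 36 active dosing periods in Any Dose, and 5 × 6 + 5 = 35 across the dose-level columns. A partial placebo doser leaves Placebo at 6 × 2 = 12.

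Even if the excluded subject has no event, the column loses information. The chance of seeing at least one event is 1 − (1 − p)^n. At p = 20% it falls from 1 − 0.8^6 = 73.8% to 1 − 0.8^5 = 67.2%. At p = 10% it falls from 1 − 0.9^6 = 46.9% to 1 − 0.9^5 = 41.0%.

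**The case against.** The best defence is that the asymmetry has a reason. SAP 3.3.2 opens by saying that members of a Dose Group share the same product and dose. A partial placebo dose is still no drug, whereas three of eight 80 mg tablets is 3 × 80 = 240 mg and not 640 mg. Grouping by treatment actually taken could justify leaving that subject out of the 640 mg column. That explains why the subject might not be labelled 640 mg. It does not justify having no dose-level column at all, which is not analysis by treatment taken either.

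On Table 10, N is already the number enrolled or randomized, and the shell prints other rows that must be zero, such as receipt of placebo under active columns. That softens the point but does not reconcile the incomplete-dose row with 3.3.2.

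The practical objections largely stand:

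- Dosing is observed and takes about five minutes, with an oral-cavity check (protocol 4.3 and 7.1.3, SAP 4.4.8).
- People who have difficulty swallowing multiple tablets are excluded.
- A stop within that window may be a swallowing problem and not a drug effect.
- The documents report no case of partial dosing.
- The safety analyses are descriptive, so no test depends on the grouping.

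These limit the importance of the gap. They do not remove it, and SAP 4.4.8 itself provides for documenting partial or interrupted dosing.

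**Conclusion.** The concern holds. Followed as written, SAP 3.3.2 takes a partial active doser out of every dose-level safety table and figure and keeps a partial placebo doser in. This departs from protocol 10.5, and SAP 15, which lists changes to the planned analyses, does not mention it.

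The loss is of attribution to a dose, in the final tables and figures only. Any Dose, the presence of the event in the AE listing, the committee review by cohort (SAP 6.6) and the halting rules (protocol 8.6) are unaffected.

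The change from 1/6 to 0/5 rests on one assumed partial doser with an event; with no partial active dosing, no result changes. It is a realistic risk only in the five groups that take two to eight tablets. The point should be corrected, but it does not threaten the conduct of the trial.

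**What to change.** In SAP 3.3.2, define each dose-level group for safety tables and figures as subjects in the stated cohort who took any quantity of VT-1598 under the stated fasting condition. Footnote every incomplete dose with the amount taken. State that Tables 9 and 10 are by assigned group. Keep the exclusion of incomplete doses for PK, where SAP 6.3.2 already has it, and keep the closing provision of 3.3.2 for subjects given a wrong dose.

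SAP 6.1 sends both safety and PK analyses to 3.3.2, so it needs a short clause saying that group membership differs between the two. The safety shells need the footnote. No new data are required: partial dosing is documented under SAP 4.4.8, and whether dosing followed the protocol is in Listing 10. PK results do not change. The drawback is that a dose column may include someone who took less than the nominal dose, which the footnote makes visible.

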3.3.3. Timepoints for Safety and PK Endpoints

Table 7 shows the analysis timepoints in the order that will appear in tables and figures along with the safety and PK endpoints measured at each timepoint for all cohorts. Endpoints analyzed by timepoint include chemistry clinical laboratory results (CHEM), hematology clinical laboratory results (HEM), coagulation clinical laboratory results (COAG), and urinalysis laboratory results (UA); VS; ECG; and blood PK and urine PK samples. Serology, toxicology, and pregnancy testing at Screening will not be included in tables or figures but will be presented in listings.

3.3.4. Baseline

Baseline for clinical laboratory results and VS will be defined as the last result obtained before study product administration. If triplicate ECG measures were performed at the same visit, baseline ECG will be defined as the mean value of the last triplicate measurements before study product administration.

Baseline height, weight, and body mass index (BMI) will be the measurements obtained at Screening. Age will be based on age at the time of enrollment.

